## **5.11 Placebo**

Placebo will be given as 500mg twice daily. Placebo will be in capsule form. It will be stored in a locked cabinet until given to the participants at room temperature in the Thomas Jefferson University Hospital Investigational Drug Service (IDS) Pharmacy.

The placebo will be packaged in bottles containing 500mg capsules. The bottle will be labeled “take one tablet twice daily until two weeks after radiation therapy ends”.

## **5.12 Receiving, Storage, Dispensing and Return**

### 5.12.1 Receipt of Drug Supplies

The study drug will be provided by the Department of Otorhinolaryngology and will be coordinated through the Thomas Jefferson University Hospital Service (IDS) Pharmacy. Upon receipt of the study treatment supplies, inventory must be performed and a drug receipt log will be filled out and signed by the person accepting the shipment. It is important that the designated study staff counts and verifies that the shipment contains all the items noted in the shipment inventory. Any damaged or unusable study drug in a given shipment (active drug or comparator) will be documented in the study files. The investigator must notify the study sponsor of any damaged or unusable study treatments that are supplied to the investigator’s site.

Upon completion or termination of the study, all unused and/or partially used investigational product will be destroyed at the site per institutional policy. It is the Investigator’s responsibility to arrange for disposal of all empty containers, provided that procedures for proper disposal have been established according to applicable federal, state, local and institutional guidelines and procedures, and provided that appropriate records of disposal are kept.

### 5.12.2 Storage

Drug will be stored in a locked cabinet until given to the participants at room temperature in the Thomas Jefferson University Hospital Investigational Drug Service (IDS) Pharmacy. The investigator must ensure that it is stored in accordance with the environmental conditions as defined in the Investigator Brochure. Clinical supplies may not be used for any purpose other than that stated in the protocol.

### 5.12.3 Dispensing of Study Drug

The study drug will be dispensed to the participants in 1 bottle containing 500mg tablets for a maximum of 8 weeks. The bottle will be labeled “take one tablet daily for three days then one tablet twice daily for three days then two tablets twice daily until two weeks after radiation therapy ends” for metformin or bottle will be labeled “take one tablet twice daily until two weeks after radiation therapy ends”. The amount of pills dispensed to every participant will be logged in the accountability logs by the pharmacist. The participant will be instructed to bring the bottle and all the pills that were not taken the day of the visit two weeks after the completion of radiation. Regular study drug reconciliation will be performed only at the end of the study.

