#### **5.8 Packaging**

The study drug will be provided by the Department of Otorhinolaryngology and will be coordinated through the Thomas Jefferson University Hospital Investigational Drug Service (IDS) Pharmacy. The study drug will be packaged in 1 bottle containing 500mg tablets for a maximum of 8 weeks.

The bottle will be labeled “take one tablet daily for three days then one tablet twice daily for three days then two tablets twice daily until two weeks after radiation therapy ends”.

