#### **5.9 Blinding of Study Drug**

The bottle will be non-descript and contain either metformin or placebo depending on randomization. Patients will be blinded to which pill (metformin or placebo) they will receive. Pill distribution will be completed by the pharmacist who will not be blinded. Principal Investigator and care providers making assessments will not be blinded.

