## **8.3 Unblinding Procedures:**

At the completion of the accrual period subjects will remain blinded until after the primary and secondary endpoints have been collected.

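### Arm-specific bottle directions and an unreconciled placebo dosage form leave the stated patient blind unprotected, which bears on the patient-reported outcomes

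*Combined protocol and SAP*

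**What the plan says.** Section 5.9 makes the claim: "Patients will be blinded to which pill (metformin or placebo) they will receive". Section 8.3 extends it in time: "subjects will remain blinded until after the primary and secondary endpoints have been collected". The measure offered in support is the container: "The bottle will be non-descript and contain either metformin or placebo depending on randomization". Section 5.9 also says openly that the dispensing pharmacist, the principal investigator and the care providers making assessments are not blinded, so the patient blind is the only one at issue here.

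The dispensing text then sets two different sets of directions. Sections 5.8 and 5.12.3 give the metformin label, whose end point is timed from the end of radiotherapy and which opens "take one tablet daily for three days then one tablet twice daily for three days then two tablets twice daily until two weeks after". Sections 5.11 and 5.12.3 give the placebo label as "take one tablet twice daily until two weeks after radiation therapy ends". The flat placebo schedule is deliberate: the Study Summary schema, section 3.1, section 5.2 and Appendix A footnote H all state that placebo has no ramp-up or escalation.

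On dosage form, section 5.8 says of the study drug: "The study drug will be packaged in 1 bottle containing 500mg tablets for a maximum of 8 weeks". Section 5.11 says "Placebo will be in capsule form" and "The placebo will be packaged in bottles containing 500mg capsules", although the label it then prescribes speaks of a tablet. The schema and sections 3.1 and 5.2 call the placebo a tab, and footnote H calls it a tablet.

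**The concern.** A patient blind needs the two treatments to be indistinguishable to the patient in what is seen, counted and read. Here the printed directions correspond one-to-one with the arm. A patient who learns that only metformin is stepped up can read the allocation from the bottle, and nothing in the plan guards against that. If section 5.11 is followed literally, a placebo patient would also find capsules in a bottle whose label says tablet.

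What is at stake is the set of outcomes that patients report themselves: the Xerostomia Questionnaire, the Multidimensional Fatigue Inventory, the MD Anderson Dysphagia Inventory and the EORTC QLQ-H&N35. The effect of metformin on xerostomia, dysphagia and fatigue is a stated secondary objective (section 2.2). Expectation can move such scores, and because investigator and assessors are unblinded by design, the patient blind is the only blinding these scores have.

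**Working it through.** The plan states no figure on this point, so there is none to reproduce. The check has two parts.

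**1. How far the directions differ.** Inputs: the two labels (sections 5.8, 5.11, 5.12.3) and the 8-week supply (sections 5.5, 5.8, 5.12.3), taken as 56 days. Total units = sum over steps of (days × units per day).

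- Metformin label: 3×1 + 3×2 + 50×4 = 3 + 6 + 200 = 209.
- Placebo label: 56×2 = 112.
- Ratio: 209/112 = 1.87.
- Days on which the daily count differs: days 1–3 (1 against 2) and days 7–56 (4 against 2), so 3 + 50 = 53 of 56. Only days 4–6 match.

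The body text describes the metformin steps less uniformly than the label. It adds +2-day windows, and the schema and sections 1.6 and 3.1 also mention reaching the top step on day 6. These wordings give:

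| Reading of the metformin steps | Units in 56 days | Days differing from placebo |
|---|---|---|
| Label: 3 days, 3 days, then top step | 209 | 53 |
| First step lasts 5 days | 5×1 + 3×2 + 48×4 = 203 | 5 + 48 = 53 |
| Second step lasts 5 days | 3×1 + 5×2 + 48×4 = 205 | 3 + 48 = 51 |
| Both steps last 5 days | 5×1 + 5×2 + 46×4 = 199 | 5 + 46 = 51 |
| Top step from day 6 | 3×1 + 2×2 + 51×4 = 211 | 3 + 51 = 54 |

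So metformin runs from about 199 to 211 units against 112, and the count differs on 51 to 54 of 56 days whichever wording is used.

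**2. Dosage form and safeguards, side by side.**

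| Item | Where | Statement |
|---|---|---|
| Metformin form | 5.8 | tablet |
| Placebo form | 5.11, description and packaging | capsule |
| Placebo form | 5.11 and 5.12.3, label | tablet |
| Placebo form | schema, 3.1, 5.2, footnote H | tab or tablet |
| Concealment | 5.9 | non-descript bottle |

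No section describes matched appearance, a common label or matched unit counts. The bottle measure covers only the container, and arm-specific directions printed on it work against it.

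**The case against.** The strongest reply is that differing labels do not strictly contradict section 5.9. Each patient sees one bottle, the label names no drug, and inferring the arm requires knowing that only metformin is stepped up. That stands. A reader might conclude that patients will be unblinded, but the documents do not show it: what patients are told depends on consent text that was not available, and no figure is given for how often a patient would guess. The unit counts show that the directions identify the arm to someone who knows both schedules; they do not measure guessing.

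Second, the capsule wording is confined to section 5.11 and may be a slip. That also stands, so it cannot be asserted that the two products look different. What can be said is that the pharmacy cannot follow both statements.

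Third, a reader might take the calls on escalation days (sections 1.6 and 5.3) as a further sign of the arm. The documents do not support that: the same sections add weekly calls, and section 6.1 arranges calls for metformin/placebo participants without distinguishing arms. At most, a clarifying sentence is wanted.

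Fourth, this is a pilot with laboratory primary endpoints. The phlebotomist is blinded (section 2.1), samples are de-identified (section 6.4.3), and secondary outcomes are analysed mainly descriptively (section 7.2). This limits the consequence but does not remove it: by-arm summaries of self-reported symptoms will still be read as comparisons.

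**Conclusion.** The point holds as an unprotected patient blind, together with one plain inconsistency on the placebo form. By the labels, the arms differ in daily count on 53 of 56 days, at 209 units against 112; allowing for the document's other wordings, 51 to 54 days and about 199 to 211 metformin units. These figures assume that the directions are followed in full over the 8-week supply.

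The consequence is confined to how the patient-reported secondary outcomes may be described and interpreted. A reader might extend it to the cytokine and exosome results or to the sample size. Nothing in the documents supports that: those endpoints are laboratory measurements, and the power calculation in section 7.4 does not depend on what patients know. The matter should be fixed, but it does not undermine the primary analysis.

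**What to change.** 1. Reconcile section 5.11 with the other passages on placebo form (schema, 3.1, 5.2, 5.12.3, footnote H), so that one form is stated throughout.
2. Reconcile the dispensing and labelling text (sections 5.8, 5.11 and 5.12.3, with the schema, 3.1, 5.2 and footnote H) with sections 5.9 and 8.3, so that neither the form nor the bottle directions identify the arm, under whatever schedule the sponsor sets. State the safeguard in section 5.9.
3. If this is not done, qualify the patient-blind claim in sections 5.9 and 8.3 and report the patient-reported outcomes as not reliably blinded.

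The first two steps cost a protocol amendment and some preparation by the pharmacy that already dispenses both products; the documents give no figure for this. The third is a change of text only, at the price of a weaker blinding claim for those outcomes.

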## Study Summary

|  |   |
|--|---|
| Title                                    | Pilot study of metformin in head and neck cancer and its effect on proinflammatory cytokines and exosomes implicated in acute and chronic toxicity   |
| Short Title                              | Metformin in radiation treatment of head and neck cancer   |
| Protocol Number                          | IRB# 16D.639/JT#9410   |
| Phase                                    | Pilot   |
| Methodology/Study Design                 | Pilot Feasibility trial   |
| Study Duration                           | 24 months   |
| Study Center(s)                          | Single Center- Jefferson  |
| Objectives                               | To assess the effect of metformin on radioprotection in normal tissue for subjects undergoing head and neck radiation. We will evaluate metformin's ability to decrease proinflammatory cytokines and decrease mucositis, xerostomia, fatigue and dysphagia.  |
| Number of Subjects                       | 50  |
| Diagnosis and Main Inclusion Criteria    | Subjects with a biopsy proven diagnosis of head and neck cancer, and who have a scheduled appointment for either postoperative adjuvant radiation or definitive radiation.  |
| Study Therapy, Dose, Route, Regimen      | Metformin is the therapeutic agent in the protocol. The initial starting dose will be 500mg orally daily for 3 (+2 days) days which then will be increased to 500 mg twice daily and, if tolerated, further increased to 1000mg twice daily after day 6 (+2 days). Subjects will maintain 1000 mg twice a day dosing until two weeks post radiation. Subjects will be randomized to 1:1 to take metformin or placebo.   |
| Duration of administration and follow-up | The initial starting dose will be 500mg orally daily for 3 (+2 days) days which then will be increased to 500 mg twice daily and, if tolerated, further increased to 1000mg twice daily after day 6 (+2 days). Subjects will maintain 1000 mg twice a day dosing until two weeks post radiation. The participant's medical records will be reviewed every 3 months for 12 months. 2 vials of Blood and 5cc of saliva samples will be obtained before, during and immediately after treatment and every three months thereafter for one year |
| Reference therapy                        | None   |

|                                |   |
|--------------------------------|---|

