**Description and justification for the route of administration, dosing regimen and treatment period:**

Metformin will be administered orally since this is the route of administration currently approved by the FDA. Beginning one-two weeks prior to planned external beam radiation therapy, the drug will be initiated at a dose of 500mg orally daily for 3 days and will then be increased to 500 mg twice daily. If tolerated, metformin will be further increased to 1000mg twice daily after day 6. Subjects will maintain 1000 mg twice a day dosing until two weeks post radiation.

There are currently multiple studies on-going using doses from between 500 mg twice daily up to 2500 mg per day in the treatment arms. There are also studies using the extended release form for a dose of 1500 mg daily. We have chosen our starting dose and escalation regimen to minimize side effects. The chosen standing dose is based on metformin's therapeutic range (minimal therapeutic dose in diabetic patients is 1500-2000 mg a day). The time of planned exposure to metformin will be 8-10 weeks. We will allow a window of an additional 2 weeks in the event that there are delays in the treatment scheduling but no patients will receive metformin for more than 12 weeks.

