#### **5.2 Treatment Regimen**

Metformin is the therapeutic agent in the protocol. The initial starting dose will be 500mg orally daily for 3 (+2 days) days which then will be increased to 500 mg twice daily and, if tolerated, further increased to 1000mg twice daily after day 6 (+ 2 days). Patients will maintain 1000 mg twice a day dosing until 2 weeks after completing their radiation. This dose schedule has been shown to be well tolerated.

The placebo will be dosed as 1 tab BID and will not have a dose escalation.

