**Rules for dose modification: Toxicity monitoring, dose modification and treatment of complications:**

Particular attention will be paid in the first three days of treatment. Patients will take 500mg/day for 3 days (+2 days). From day 4, 500mg twice daily and then in 3 days (+2 days) dose escalation to 1000mg twice daily will be achieved. This will be taken until the day before surgery after dinner. A phone call on the day of each dose escalation will be made in order to evaluate the tolerability of the drug and also weekly thereafter. Patients will be instructed to contact the clinical investigators should any toxicity occur during the study.

Metformin will not be started if CT scan with intravenous contrast is scheduled. After the scan they will be instructed to start the metformin the following day. This approach is more stringent than the most recent recommendation of the American College of Radiology which does not recommend holding metformin in the absence of comorbidities (renal insufficiency, liver dysfunction, alcohol abuse, cardiac failure, myocardial or peripheral muscle ischemia, sepsis or severe infection) which are exclusion criteria for this clinical trial.

Toxicity will be evaluated using the most recent version (version 3) of the NCI toxicity criteria, i.e. the NCI Common Terminology Criteria for Adverse Events (CTCAE) version 4.0. The CTCAE provides descriptive terminology and a grading scale for each adverse event listed. A copy of the CTCAE can be found at <http://ctep.cancer.gov>.

Grade 1 toxicity: Patient will be maintained on full dose.

Grade 2 toxicity: Dose will be reduced by 50% until grade 1 or lower. If symptoms are not resolved within 3 days the treatment will be discontinued definitively.

Grade 3 toxicity (probably or definitely drug related): Treatment will be interrupted and toxicity reassessed daily. If toxicity improves to grade 2, dose will be reduced by 50%.

Grade 4 toxicity (probably or definitely drug related): Treatment will be discontinued definitively.

In case of grade 1 or 2 diarrhea (the most frequent side effect) a concomitant administration of loperamide will be provided.

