#### **5.5 Preparation and Administration of Study Drug/Therapy**

Metformin tablets will be provided by the Department of Otorhinolaryngology and will be coordinated through the Thomas Jefferson University Hospital Investigational Drug Service (IDS) Pharmacy. Drug will be stored in locked cabinet until given to the participants. An 8 week supply of metformin will be provided to subjects and the drug will be self-administered by the participants.

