## **6.3 Dose Delays and Dose Modifications**

Toxicity will be evaluated using the most recent version (version 4) of the NCI toxicity criteria, i.e. the NCI Common Terminology Criteria for Adverse Events (CTCAE) version 4.0. The CTCAE provides descriptive terminology and a grading scale for each adverse event listed. A copy of the CTCAE can be found at <http://ctep.cancer.gov>.

Grade 1 toxicity: Patient will be maintained on full dose.

Grade 2 toxicity: Dose will be reduced by 50% until grade 1 or lower. If symptoms are not resolved within 3 days of toxicity development the treatment will be interrupted definitively.

Grade 3 toxicity (probably or definitely drug related): Treatment will be interrupted. Toxicity will be evaluated daily and if toxicity improves to grade 1 or lower dose will be reduced by 50%. If toxicity is not improved or resolved or reduced to grade 1, treatment will be interrupted definitively.

Grade 4 toxicity (probably or definitely drug related): Treatment will be permanently discontinued.

In case of grade 1 or 2 diarrhea (the most frequent side effect) a concomitant administration of loperamide will be provided.

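### The metformin label moves self-dosing patients to 2000 mg/day without condition; the regimen requires tolerance first, and no text puts the check call before the higher dose

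*Combined protocol and SAP*

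**What the plan says.** **Label.** Section 5.12.3 gives the metformin bottle wording as "take one tablet daily for three days then one tablet twice daily for three days then two tablets twice daily until two weeks after radiation". Section 5.8 has the same text: "then one tablet twice daily for three days then two tablets twice daily until two weeks after radiation therapy ends". Neither mentions tolerance, and neither tells the patient to wait for a call. Under 5.5, "the drug will be self-administered by the participants".

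**Regimen.** The top step is conditional in four places. Section 1.6 says "If tolerated, metformin will be further increased to 1000mg twice daily after day 6". The Study Summary, 5.2 and Appendix A note G carry the same condition and add a +2 day window; 5.2 reads "if tolerated, further increased to 1000mg twice daily after day 6 (+ 2 days").

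**Checks.** Sections 1.6 and 5.3 plan a telephone call on the day of each escalation, to assess tolerability, and then weekly calls. Section 6.1 arranges call times with participants and tells them to report side effects. Section 5.6 supplies dosing instructions with the bottle that follow the dosing stated earlier in the protocol. If toxicity becomes known, 6.3 applies: "Grade 2 toxicity: Dose will be reduced by 50% until grade 1 or lower".

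**Text closer to the label.** The dose-modification rules in 5.3 state the step without condition: "From day 4, 500mg twice daily and then in 3 days (+2 days) dose escalation to 1000mg twice daily will be achieved". The Study Summary schema, the corresponding rules in 1.6 and the schema in 3.1 place the step at day 6 rather than after it.

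**The concern.** A patient at home with one bottle already holds the tablets for the higher dose, and the bottle is the instruction in front of them. The protocol prescribes its wording, so the missing condition is not left for the pharmacy to add. If the escalation-day call is late or missed, a patient who is not tolerating 500 mg twice daily can follow the label exactly and take a step that the regimen withholds.

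At stake are avoidable gastrointestinal toxicity and possibly an avoidable stop of study drug. Safety and tolerability is a secondary objective (2.2), so it matters that the dose taken is the dose the protocol intends. No sample size, power or error-rate figure is involved.

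**Working it through.** No stated figure needs reproducing. The check is a dose count and a comparison of texts.

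**1. Dose by day under the label** (500 mg tablets, 5.8 and 5.12.3)

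| Days | Label | mg/day |
|---|---|---|
| 1–3 | 1 tablet once daily | 1 × 500 = 500 |
| 4–6 | 1 tablet twice daily | 2 × 500 = 1000 |
| 7 onward | 2 tablets twice daily | 2 × 2 × 500 = 2000 |

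**2. Day of the top step.** The label gives 3 + 3 = 6 days and so day 7. After day 6 with +2 days means day 7, 8 or 9. Day 7 lies inside that range, so the day is not an error. The label simply gives the patient no room to wait.

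**3. The day 6 wording.** Twice-daily dosing starts on day 4, and three days of it are days 4, 5 and 6. Day 6 cannot be both the third day at 1000 mg and the first at 2000 mg. The Study Summary schema, the rules in 1.6 and the schema in 3.1 therefore conflict with 5.2 and with the label.

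**4. Size for one patient.** If the step is not tolerated, the intended dose stays at 1000 mg/day and the label gives 2000 mg/day: 2000 / 1000 = 2.

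**5. Does any other text supply the condition in time?**
- *Escalation-day call (1.6, 5.3):* same day, but its order relative to the first higher dose is not given. A patient could take two tablets in the morning and be called in the afternoon.
- *Instructions with the bottle (5.6):* their text is not in the documents. The dosing stated earlier is mixed, conditional in 5.2 and unconditional in 5.3, so they may or may not carry the condition.
- *Side-effect reporting (1.6, 5.3, 6.1):* this relies on the patient calling, and no text tells the patient to hold the step meanwhile.
- *Medication inventory (6.1):* the first is in week 3 of radiation, too late for this step.

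Each reduces the risk. None makes the step depend on a completed check.

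**The case against.** The case for leaving this alone is reasonable. A call on the day of escalation, made to judge tolerability, is most naturally read as informing that escalation. The bottle instructions probably follow 5.2, condition included. A label normally states the default schedule, with dose changes handled elsewhere. The dose at issue is the trial's own target, at the top of the 1500–2000 mg/day that 1.6 calls the minimal therapeutic dose in diabetic patients. Section 1.6 describes the commonest toxicity as minor.

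Most of this stands, and it limits the weight of the point. It does not remove the conflict: one prescribed text tells the patient to take a step that four others make conditional, and the intended check has no stated place before the dose.

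Three stronger readings are tempting, and the documents do not support them.
- A reader might turn the 1–5% side-effect rate in 1.6 into a chance that some of the 25 metformin patients will be wrongly escalated. That rate carries no grade, dose or timing, includes patients who may need no hold (grade 1 toxicity keeps the full dose), and says nothing about how often the safeguards fail.
- A reader might compare 2000 mg/day with the halved dose required for grade 2 toxicity. If the team had ordered the halved dose, it would already have overridden the label. If it did not know of the toxicity, no halved dose was in force.
- A reader might infer that placebo patients, who have no escalation, get no early calls. Section 6.1 arranges tolerability calls with participants in general and does not limit them to one arm.

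**Conclusion.** The conflict is real and worth correcting. Its expected harm is small and mainly gastrointestinal. For a patient who does not tolerate 500 mg twice daily, the label gives twice the intended dose until the study team reaches the patient or the patient calls in. How many patients that would be cannot be estimated from the documents. This rests on two assumptions: that patients follow the bottle, and that the unseen instructions in 5.6 do not already tell them to wait. If those instructions do, the label should still agree with them. The primary analysis and sample size are not affected.

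**What to change.** 1. In 5.8 and 5.12.3, change the last part of the metformin label to: *then, if the study team confirms you are tolerating it, two tablets twice daily until two weeks after radiation therapy ends*.
2. In 1.6 and 5.3, state that the escalation-day call is made before the first higher dose, and that a missed call is repeated within the +2 day window. The dosing text in 1.6 does not give that window, so the new sentence there should name it.
3. In the Study Summary schema, the dose-modification rules in 1.6 and the schema in 3.1, replace the day 6 wording with after day 6.

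**Cost.** The changes are one clause on the label, one sentence in each of two sections, three small wording corrections and the occasional repeat call. There are two downsides.
- A missed call could keep a tolerant patient at 1000 mg/day for up to about two more days. That is below the 1500 mg/day under which 1.3 and 1.5 say clinically significant responses are generally not seen. Against a planned exposure of 8–10 weeks (56–70 days), two days is 2/70 to 2/56, about 3% to 4%. The repeat-call rule is there to hold it to that.
- The metformin label gains one more line that the placebo label lacks. The two labels already differ, so this adds to an existing difference and does not create a new kind.
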